5.0 Evaluation During Study

- 5.1 Evaluations during SGI-110 cycles
 - 5.1.1 To be done within 72 hours of each cycle and if clinically indicated, on the third day of each cycle and once per week in the second and third week of each cycle: CBC, differential, platelet, SGPT, bilirubin, creatinine, electrolytes, serum or urine pregnancy test for women with reproductive potential.

Other laboratory tests can be performed as medically indicated.

5.2 Evaluations prior to DLI administration

To be done within 72 hours of each cycle and if clinically indicated, on the third day of each cycle and once in the second and third week: CBC, differential, platelet, SGPT, bilirubin, creatinine, electrolytes.

5.3 Response Evaluation:

Disease status evaluations follow standard practice. If clinically indicated, these studies may be done at other time points, which can replace the nearest planned time point.

For cohorts 1 and 2:

- 5.3.1 To be done after 2nd, 4th, and 6th cycles of SGI-110.
- 5.3.2 After the patients are documented to achieve response, further disease status evaluation will be performed when it is clinically indicated.
- 5.3.3 Disease status will include:
 - 5.3.1.1 Bone marrow aspirate and biopsy with cytogenetics, FISH, flow and molecular studies.
 - 5.3.1.2 Chimerism studies from peripheral blood
- 5.3.4 If a patient shows no evidence of response in the absence of disease progression after the second cycle of SGI-110 (Day 28 +/-7 days), further bone marrow aspirate and/or biopsy will be scheduled to document response at the end of Cycle 4 (Day 28 +/-7 days).
- 5.3.5 If a patient shows no evidence of response in the absence of disease progression even after the fourth cycle of SGI-110 (Day 28 +/-7 days), further bone marrow aspirate and/or biopsy will be scheduled to document response at the end of Cycle 6 (Day 28 +/-7 days).
- 5.3.6 If the patient does not show evidence of response at the end of Cycle 6, the patient

- will be taken off the study with no further follow-up.
- 5.3.7 Bone marrow evaluations and peripheral blood chimerism studies can be ordered more frequently if clinically indicated.

For cohort 3:

- 5.3.8 Disease status evaluations follow standard practice with day +100, Month 6, and 1-year disease evaluations.
- 5.3.9 Disease status evaluation will include:
 - 5.3.9.1 Bone marrow aspirate and biopsy with cytogenetics, FISH, flow and molecular studies.
 - 5.3.9.2 Chimerism studies from peripheral blood.
- 5.4 Outside Physician Participation During Treatment

This will be performed only after the patients are documented to show evidence of response with the therapy (morphological CR for cohort 1 and MRD negative status for cohort 2 respectively). DLI administrations will only be performed at MDACC.

- 5.4.1 MDACC Physician communication with the outside physician is required prior to the patient returning to the local physician. This will be documented in the patient record.
- 5.4.2 A letter to the local physician outlining the patient's participation in a clinical trial will request local physician agreement to supervise the patient's care and perform certain laboratory tests (see Appendix D.).
- 5.4.3 Protocol required evaluations outside MDACC will be documented by telephone, fax or e-mail. Fax and/or e-mail will be dated and signed by the MD Anderson physician, indicating that they have reviewed it.
- 5.4.4 A copy of the informed consent, protocol abstract, treatment schema and evaluation during treatment will be provided to the local physician.
- 5.4.5 Documentation to be provided by the local physician will include progress notes, reports of protocol required laboratory and diagnostic studies and documentation of any hospitalizations.
- 5.4.6 The home physician will be requested to report to the MDACC physician investigator all SAE's within 24 hours of documented occurrence.

Communication of protocol required evaluations can be by telephone, fax, or e-mail. Patients will return to MDACC at least every 3 months for evaluation. The Study Chair or treating physician must review the laboratory results, determine clinical significance, and sign and date the report. Concomitant medications will be captured in the electronic medical record.

5.5 Follow-Up Evaluations

Follow-Up evaluations will be performed per AML or MDS standard of care as appropriate.

6.0 Criteria for Response

- 6.1 Response definition:
 - 6.1.1 For patients with documented morphological relapse at study entry:

- 6.1.1.1 Clinical response and hematological improvement for patients with myelodysplastic syndrome will be determined according to the 2006 International Working Group recommendations.
 - 6.1.1.1.1 Complete remission (CR): Bone marrow with </= 5% bone marrow blasts with normal maturation of all cell lines; a peripheral blood granulocyte count >/= 1 X 10⁹/L and a platelet count >/= 100 x 10⁹/L
 - 6.1.1.1.2 Marrow CR: Bone marrow has </=5% myeloblasts and decrease by >/=50% over pretreatment.
 - 6.1.1.1.3 Partial remission (PR): patients must demonstrate all CR criteria if abnormal before treatment except that marrow blasts should decrease by 50% or more compared with pretreatment levels, or patients may demonstrate a less-advanced MDS disease classification category than prior to treatment.
- 6.1.1.2 Clinical response for patients with acute myeloid leukemia will be based on revised recommendations of the 2003 International Working Group.
 - 6.1.1.2.1 Morphologic complete remission: Bone marrow with <5% blasts in the absence of extramedullary disease in addition to a peripheral blood granulocyte count >/= 1 X 10°/L and a platelet count >/= 100 x 10°/L.
 - 6.1.1.2.2 Partial remission (PR): This designation requires all of the hematologic values for a CR but with a decrease of at least 50% in the percentage of blasts to 5% to 25% in the bone marrow aspirate.
 - 6.1.1.2.3 Morphological complete remission with incomplete count recovery (CRi): Bone marrow blast count <5%.
- 6.1.2 For patients with persistent or recurrent disease by molecular, cytogenetic or flow cytometry findings without morphologic remission at study entry; disappearance of leukemia clone by repeat studies.
- 6.1.3 For cohort 3, response will be remaining in morphological remission without evidence of minimal residual disease by flow-cytometry, cytogenetics or molecular findings.
- 6.2. No response:
 - 6.2.1 Any response less than a partial response.
- 6.3 Progression:
 - 6.3.1 For patients with documented morphological relapse at study entry; bone marrow blast count more than 60% and/or new extramedullary sites.
 - 6.3.2 For patients with persistent or recurrent disease by molecular, cytogenetic or flow cytometry findings despite morphologic remission at study entry; evidence of morphologic relapse.
 - 6.3.3 For cohort 3, any disease progression with either morphological relapse and/or

evidence of minimal residual disease with flow-cytometry, cytogenetics or molecular testing.

7.0 Statistical Considerations

This is a single-arm phase IIA activity trial of SGI-110 in combination with or without DLI given post allogeneic stem cell transplant for patients with hematologic malignancies. There will be three patient subgroups, patients with minimal residual disease (MRD), and patients who have relapsed (REL) and patients who receive SGI-110 as maintenance. The phase IIA design of Thall and Sung (41) will be used to monitor the response rate within each subgroup. In the MRD subgroup, response will be defined as resolution of MRD with SGI-110. In the REL subgroup, clinical response to SGI-110 for patients with myelodysplastic syndrome will be determined according to the 2006 International Working Group recommendations and for patients with acute myeloid leukemia will be based on revised recommendations of the 2003 International Working Group. For the maintenance cohort (cohort #3), that will be relapse free survival at 1-year.

Disease and Treatment Regime. This is a single-arm phase IIA activity trial of SGI-110 in combination with or without DLI given post allogeneic stem cell transplant (allosct) for patients with hematologic malignancies. There will be three patient subgroups. The first subgroup will be patients with minimal residual disease (MRD). The second subgroup will be patients who have relapsed (REL). The third group will be high risk patients who will receive the intervention for maintenance. The phase IIA design of Thall and Sung (41) will be used to monitor the response rate within each subgroup. The two differences between the subgroups are in terms of (i) entry criteria and (ii) definition of response.

7.1 Cohort 1 and 2: The same phase IIA design will be used for cohort 1 and 2, as follows: A response probability of .20 or larger will be considered promising. A maximum of 25 patients with will be treated in each group. Accrual will be stopped due to futility if less than or equal to 0/8 or 1/20 responses are observed. A patient may have therapy temporarily postponed for up to 56 days due to toxicity. Any patient whose therapy has been started and later permanently discontinued due to the following will be counted as a treatment failure, that is, a non-responder: 1) progressive disease, or 2) due to death, or 3) dropout, or 4) physician decision that it is futile to continue, or 5) severe toxicity prior to achieving disease remission. Patients who do not complete the first cycle of treatment will be considered as non-evaluable. Secondary outcomes will include disease-free survival (DFS) time, overall survival (OS) time, graft-versus-host disease, safety and duration of remission. Within each subgroup (MRD and REL), these events will be tabulated and the distributions of DFS and OS time estimated using the method of Kaplan and Meier (42).

Patients with MRD. In this subgroup, response will be defined as resolution of MRD, at any time point within the first 6 cycles of SGI-110 treatment. A response probability of .20 or larger will be considered promising. A maximum of 25 patients with MRD will be treated. Denoting p = Pr(response), it will be assumed that p follows a beta(.20, .80) prior. Accrual will be stopped due to futility if Pr(p > .20 | data) < .02. This implies that accrual of patient with MRD will be stopped with SGI-110 declared not promising in these patients if less than or equal to 0/8 or 1/20 responses are observed. If necessary, accrual will be suspended after 8 or 20 patients have been treated in order to apply the stopping rule. For example, if there have been 0/7 responses and patient #8 has been treated but not yet been fully evaluated at 4 months, then accrual will be suspended until that patient's outcome has been evaluated. If patient #8 has a response, then patients #9 - #20 may be treated. If patient #8 does not have a response, then accrual of

MRD patients will be terminated. The operating characteristics of this rule are as follows. Computations were carried out in Multc99.

Table 1. Operating characteristics of the rule for monitoring response in MRD patients.

True Pr(Response)	Prob(Stop early)	Achieved Sample Size Quartiles
.05	.82	8 8 20
.10	.54	8 20 25
.15	.32	8 25 25
.20	.18	25 25 25

Patients who have relapsed (REL). In this subgroup, response will be defined as disease remission at any time point within the first 6 cycles of therapy with SGI-110. Otherwise, the same design as that used in the MRD subgroup will be used.

7.2. High Risk Patients. This cohort will include high risk patients with one-year relapse incidence of 35%-45%. They will receive maintenance therapy with SGI for one year. A maximum of 40 patients will be enrolled. The primary endpoint for this cohort will be relapse-free survival (RFS) time. The Bayesian method of Thall et al will be used to monitor RFS time in this cohort (41). We denote the standard historical therapy by S and the experimental SGI-110 therapy by E. We assume that TS=time to disease progression or death in this cohort associated with standard therapy follows an exponential distribution with median mS and that TE=time to disease progression or death in these patients associated with the experimental SGI-110 therapy follows an exponential distribution with median mE. We denote the median RFS times for the standard and experimental therapies by mS and mE, respectively. Under a Bayesian model, both mS and mE are assumed to follow Inverse Gamma (a, b) priors, denoted IG(a, b). From historical data, Pr(TS > 12 months) = .35, which implies that the historical median RFS = 7.9 months in this group under the assumption of exponentially distributed RFS times. For priors, we assume that $mS \sim IG$ (17.6, 131.2), which has mean = 7.9 months and variance = 4.0 months. We assume that mE ~ IG (3, 15.8), which has the same mean = 7.9months but a much larger variance = 62.4. We will monitor possibly right-censored TE continuously through the trial and will terminate accrual to this cohort if at any time:

$$Pr(mS < mE \mid data) < 0.07.$$

The accrual rate in this cohort is expected to be 2 patients per month. We will follow patients until all patients in the cohort have been followed for two years after transplant. We will enroll a maximum of 40 patients in this cohort.

Operating Characteristics. The operating characteristics of this stopping rule under the assumptions above were obtained by simulating the trial 2000 times each using the program One-Arm TTE v 3.0.6. These are summarized the table below.

Operating Characteristics of the Stopping Rule for Maintenance Patients

True Median RFS (months)	True Pr (RFS > 12 months)	Pr (Stop Early)	Mean Sample Size
4.4	.15	.827	21.8

6.0	.25	.339	32.5
7.9	.35	.103	37.3
10.4	.45	.036	39.0
13.9	.55	.009	39.7

Secondary outcomes. Secondary outcomes will include disease-free survival (DFS) time, relapse free survival (RFS), overall survival (OS) time, graft-versus-host disease, safety and duration of remission. Within each subgroup, these events will be tabulated and the distributions of RFS and OS time estimated using the method of Kaplan and Meier (42).

7.3 Cross-over. Patients treated on cohort #2 (patients with minimal residual disease while in morphological remission and cohort #3 (maintenance treatment cohort) will be allowed to receive higher doses of SGI-110 if they progress while on therapy with the study drug. Patients who are considered for cross-over to another study cohort due to progression of disease with an aim to receive higher doses of SGI-110 will be screened for the eligibility of that study cohort prior to initiation of higher doses of study drug. The subgroup of cross-over patients will be followed for evaluation of subsequent outcomes, such as response OS, starting from the date of cross-over.

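### Section 7.1 classes a treated patient lost in cycle 1 both as a non-responder and as non-evaluable; if the second rule is applied, early failures leave the response rate and the futility rule

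*Combined protocol and SAP*

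**What the plan says.** Section 7.1 judges cohorts 1 and 2 on a single-arm response rate: "A response probability of .20 or larger will be considered promising". The prior and futility criterion are given for the MRD subgroup: "it will be assumed that p follows a beta(.20, .80) prior" and "Accrual will be stopped due to futility if Pr(p > .20 | data) < .02". These yield the boundaries in "Accrual will be stopped due to futility if less than or equal to 0/8 or 1/20 responses are observed". The relapsed subgroup uses the same design.

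The counts are worded in treated patients: "A maximum of 25 patients with MRD will be treated", and "accrual will be suspended after 8 or 20 patients have been treated in order to apply the stopping rule".

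Two consecutive sentences then classify patients who stop early:

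- "Any patient whose therapy has been started and later permanently discontinued due to the following will be counted as a treatment failure". The listed reasons are progression, death, dropout, a physician's judgement that continuing is futile, and severe toxicity before remission.
- "Patients who do not complete the first cycle of treatment will be considered as non-evaluable". No reason is named and no exception is made.

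The plan does not say which sentence takes precedence, what completing the first cycle means, whether non-evaluable patients are replaced, or whether an all-treated analysis will be reported.

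**The concern.** A patient who receives SGI-110 and then dies, progresses, drops out or stops for severe toxicity during cycle 1 is a non-responder under one sentence and non-evaluable under the next.

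The choice matters because the excluded patients are nearly all failures. The first scheduled response assessment in both cohorts follows cycle 2 (sections 4.2.1.2 and 4.2.2.2), so a patient lost in cycle 1 will rarely have a documented response. Removing such patients shrinks the denominator and leaves the numerator almost unchanged.

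The primary endpoint is a single-arm rate read against .20, with futility looks at only 8 and 20 patients and at most 25 per cohort. A few reclassified patients can change the reported rate and a stopping decision. The trial is single-arm, and the plan leaves the choice open, so it could be made after outcomes are known.

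**Working it through.** **Inputs from section 7.1.** Prior beta(.20, .80); stop if Pr(p > .20 | data) < .02; boundaries 0/8 and 1/20; maximum 25. Table 1 gives early-stopping probabilities of .82, .54, .32 and .18 at true rates .05, .10, .15 and .20.

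**Assumed input.** q is the share of treated patients who do not complete cycle 1. The documents give no figure, so a range of 0 to 25% is shown.

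**Step 1: reproduce the boundaries.** With r responses in n patients the posterior is beta(.20 + r, .80 + n − r).

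| Data | Pr(p > .20) | Against .02 |
|---|---|---|
| 0/7 | .0206 | continue |
| 0/8 | .0153 | stop |
| 1/19 | .0223 | continue |
| 1/20 | .0180 | stop |

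The stated boundaries are confirmed.

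**Step 2: reproduce Table 1.** The first look stops with no responses in 8. The second stops, given that the first was passed, only if there was exactly one response in the first 8 and none in the next 12. So

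Pr(stop early) = (1 − p)^8 + 8p(1 − p)^19.

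At p = .15 this is .2725 + .0547 = .327. At .05, .10, .15 and .20 it gives .814, .539, .327 and .191, within about .01 of Table 1.

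**Step 3: drop cycle-1 failures.** If a share q of treated patients is removed and none of them responded, the monitored rate is p/(1 − q). Putting that into the formula, with looks at 8 and 20 evaluable patients:

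| q (assumed) | p = .15 monitored as | Stop, p = .05 | Stop, p = .10 | Stop, p = .15 | Stop, p = .20 |
|---|---|---|---|---|---|
| 0 | .150 | .814 | .539 | .327 | .191 |
| 2% | .153 | .809 | .528 | .317 | .182 |
| 5% | .158 | .800 | .513 | .301 | .170 |
| 10% | .167 | .783 | .485 | .274 | .149 |
| 20% | .188 | .743 | .423 | .219 | .109 |
| 25% | .200 | .720 | .389 | .191 | .090 |

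At q = 25%, a treatment with a true all-treated rate of .15 is monitored exactly like one at the promising threshold.

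**Step 4: single cases.**

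- 8 treated, no responses, 1 death in cycle 1: counting all gives 0/8 and a stop; excluding gives 0/7, where the criterion is not met.
- 20 treated, 1 response, 3 cycle-1 failures: counting all gives 1/20 (.0180, stop); excluding gives 1/17 (.0342, continue).
- 25 treated, 4 responses, 5 cycle-1 failures: 4/25 = 16% becomes 4/20 = 20%.

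**The case against.** The strongest reply is that the two sentences can be read as a general rule and a carve-out: stopping after cycle 1 is failure, and patients who never finish cycle 1 are outside the evaluable set. The text does not say this, and the failure rule covers anyone whose therapy has started. The reading removes the contradiction only by making the outcome-dependent exclusion explicit.

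The points about size have more force:

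- **q may be small.** SGI-110 is given on days 1 to 5 of a 28-day cycle. If completing the cycle means completing the injections, few patients are affected. Section 4.2.1.8 also restricts early removal in cohort 1. At q of 5% or less, the stopping probabilities move by under 3 points.
- **Step 3 assumes looks at 8 and 20 evaluable patients.** The plan words them in treated patients and does not mention replacement. With 25 treated, 20 evaluable patients are reached with probability of about .62 at q = 20% and .38 at q = 25%. The high-q rows therefore often describe a trial that treats more than 25.
- **0/7 is not a scheduled look.** If the trial waits for an eighth evaluable patient, the stop is usually delayed by one patient and is avoided only if that patient responds.
- **Section 7.1 has no final efficacy test.** Early deaths would still appear in overall survival and safety.

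These points stand as limits on the magnitude. None reverses the direction: exclusion raises the response rate and weakens futility stopping.

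**Conclusion.** The concern holds. The two sentences give incompatible classifications of the same patient on the primary endpoint of cohorts 1 and 2, and the plan does not resolve them. Applying the non-evaluable rule biases the response rate upward by a factor of 1/(1 − q) and lowers the chance of stopping for futility. The effect is nil at q = 0, modest at 5%, and material at 10% to 25%. It rests on q, which is assumed, and on patients lost in cycle 1 having no documented response. Cohort 3, whose endpoint is relapse-free survival, is not affected. Because the rule decides who counts in the primary endpoint, it must be corrected before the response rates are analysed.

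**What to change.** In section 7.1, delete the non-evaluable sentence or limit it to patients who never received SGI-110. State that every patient given at least one dose counts in the response denominator, in the maximum of 25 and at the 0/8 and 1/20 checks, and that a patient whose treatment ends before a response is documented is a non-responder. This goes slightly beyond the five listed reasons, so the failure definition should be reworded to match. A rate among patients who completed cycle 1 may be kept as a labelled sensitivity analysis, with completion defined.

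The cost is a change of a sentence or two. It fits the existing wording in treated patients and leaves the boundaries and Table 1 as they are. The reported response rate may be somewhat lower. The change concerns counting only and does not touch patient management.

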1.3.2 Secondary Endpoints

The secondary endpoints are:

- 1.3.2.1 Safety (type, frequency, severity of AEs and relationship of AEs to SGI-110)
- 1.3.2.2 Overall response rate
- 1.3.2.3 Duration of remission
- 1.3.2.4 Incidence of acute and chronic graft versus host disease (GVHD)
- 1.3.2.5 Overall survival and disease free survival at one year after study enrollment

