- 4.2.1.3 Patients who do not achieve CR/CRi within the first 2 cycles of SGI-110 and still have less than 30% bone marrow bone marrow blasts will continue to receive SGI-110 with an intent to achieve CR.
- 4.2.1.4 Patients who do not achieve CR/CRi within the first 4 cycles of SGI-110 and still have less than 30% bone marrow bone marrow blasts will have the option to receive two more cycles of SGI-110 with an intent to achieve CR if the patient, treating physician and principal investigator determine such an action as the best interest of the patient.
- 4.2.1.5 Patients who do not achieve CR/CRi after the fourth cycle of SGI-110 will be taken off the study if the patient, treating physician and principal investigator do not determine continuation of SGI-110 for 1-2 more cycles with an intent to achieve CR as the best interest of the patient.
- 4.2.1.6 Any patient who does not achieve response after a maximum use of six cycles of SGI-110 will be taken off the study.
- 4.2.1.7 Patients who are reported to achieve CR/CRi at any response assessment time points will continue the study drug, SGI-110, as maintenance therapy at the subsequent treatment cycles.
 - 4.2.1.7.1 The starting maintenance dose will be 40 mg/m2/day (dose level 1) for patients who achieved CR/CRi with doses higher than 40 mg/m2/day.
 - 4.2.1.7.2 The starting maintenance dose will be at least one dose level lower than the treatment dose that led the patient to achieve CR/CRi if the patient was on 40 mg/m2/day dose or less during treatments with active disease.
- 4.2.1.8 Patients will not be taken off therapy with SGI-110 prior to completion of the first 4 courses unless for unequivocal disease progression while on therapy, unacceptable toxicities, or patient request.
- 4.2.1.9 During the treatment cycles given with the intent to achieve CR (patient has active disease), the dose of SGI-110 can be decreased at least by

- one dose level (presented at Section 4.4.4) at the discretion of the treating physician or principal investigator if:
- 4.2.1.9.1 There are grade 3-4 reversible non-hematological toxicities attributable to the drug observed.
- 4.2.1.9.2 Dose change is considered in the best interest of the patient.
- 4.2.1.10 For patients who achieve CR/CRi, treatment with SGI-110 will be continued as maintenance therapy until treatment failure or for a maximum of 12 cycles of SGI-110 treatment.

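### GVHD incidence in cohorts 1 and 2 has no time horizon or estimator, and the protocol contradicts itself on whether non-responders are followed for GVHD; if they are not, a crude proportion reads low

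*Combined protocol and SAP*

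**What the plan says.** Section 1.3.2.4 names the incidence of acute and chronic GVHD as a secondary endpoint and gives no time at which it is to be read. The next item, for survival, does give one: "Overall survival and disease free survival at one year after study enrollment".

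Section 7.1 lists GVHD among the secondary outcomes of cohorts 1 and 2 and says "Within each subgroup (MRD and REL), these events will be tabulated". The same sentence keeps Kaplan-Meier for DFS and OS. The paragraph on secondary outcomes that closes Section 7.2 follows the same pattern: "Within each subgroup, these events will be tabulated and the distributions of RFS and OS time estimated". No denominator, time origin, censoring rule or competing event is given for GVHD.

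The sections on follow-up point in different directions:

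- Section 5.3.6 (cohorts 1 and 2): a patient without response at the end of cycle 6 "will be taken off the study with no further follow-up".
- Section 4.2.1.6 (cohort 1): "Any patient who does not achieve response after a maximum use of six cycles of SGI-110 will be taken off the study". Section 4.2.1.5 allows a cohort 1 non-responder to leave the study after cycle 4.
- Section 8.4 counts six-cycle non-response as a reason to discontinue study treatment. It requires that everyone who discontinues treatment, whatever the reason, still be followed for GVHD and survival. It then exempts subjects who discontinue from the study from the effort to collect all data.
- Section 5.5 leaves follow-up to standard of care, with no length for cohorts 1 and 2. Section 7.2 does set a length for cohort 3: until all its patients have reached two years after transplant.

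**The concern.** A count of GVHD cases over all treated patients is an incidence only if everyone is observed to the same horizon or has died before it. A non-responder who leaves after cycle 4 or 6 without GVHD would count as GVHD-free for the whole period, although nobody looked afterwards. GVHD is a key safety outcome of DLI: the two retrospective series in Section 2.8 report it in 41% and 60% of patients. A proportion lowered by short observation would make SGI-110 with DLI look safer than it is.

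**Working it through.** 1. **The plan's own figures.** No figure is stated for GVHD incidence, its precision or its follow-up. The computed design figure in Section 7.1 is Table 1. With stopping at 0/8 or 1/20, Pr(stop) = (1−p)^8 + 8p(1−p)^19. This gives .814, .539, .327 and .191 at p = .05, .10, .15 and .20, against the stated .82, .54, .32 and .18. The table reproduces, and nothing below changes it or the maximum of 25 patients.

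2. **Calendar.** With 28-day cycles (Section 4.2), six cycles last 168 days, or 5.6 months of 30 days. Section 4.6 plans DLI on day 6 of cycles 2, 4 and 6: day 28 + 6 = 34 for the first and day 140 + 6 = 146 for the third. A patient who leaves at day 168 has been seen for 134 days (about 19 weeks) after the first DLI and 22 days after the third. Adverse event recording does not fill the gap. Section 8.1 covers related events to 30 days after the last dose. Section 8.3 covers SAEs to the same point, and later ones only if suspected to be drug-related.

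3. **Crude proportion if Section 5.3.6 governs.** Assumptions: true 12-month incidence G; constant hazard λ = −ln(1−G)/12; a fraction c leaves at 5.6 months regardless of GVHD risk. The documents give no c. The levels of G are rates cited in the protocol: 17% chronic and 37% acute with azacitidine plus DLI (Section 2.8), and 37% chronic with azacitidine maintenance (Section 2.0). Crude = (1−c)G + c[1 − exp(−5.6λ)].
   - G = 17%: λ = .01553, and 1 − exp(−.0870) = .0833.
   - G = 37%: λ = .03850, and 1 − exp(−.2156) = .1940.

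   | c | G = 17% | G = 37% |
   |---|---|---|
   | .30 | 14.4% | 31.7% |
   | .50 | 12.7% | 28.2% |
   | .75 | 10.5% | 23.8% |

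   Out of 25 patients, the shortfall is 0.6 to 1.6 patients at 17% and 1.3 to 3.3 at 37%.

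4. **Adding deaths.** The formula has no deaths, so this was simulated with constant hazards, a death hazard set to 50% or 70% survival at 12 months, and 30% to 80% leaving. Crude was 11–15% against 17% and 24–33% against 37%. Cumulative incidence with death as a competing event recovered 17% and 36–38%. One minus Kaplan-Meier, censoring deaths, overshot at 20–23% and 43–50%.

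5. **If Section 8.4 governs to 12 months.** With no loss to follow-up, the same simulation gives crude equal to cumulative incidence, at 17% and at 37%. Deaths alone do not bias the crude figure.

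6. **If exit is related to GVHD risk.** With leavers at half the GVHD hazard and twice the death hazard (80% leaving, 50% survival), cumulative incidence is too high: 11.4% against a true 8.8%, and 25.6% against 20.7%. With leavers at 1.5 times the GVHD hazard, it is slightly low: 17.4% against 18.4%, and 36.9% against 38.3%.

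7. **Precision.** With 25 patients, half leaving and 50% survival, the standard deviation of the crude proportion is 6.8 points at 17% and 9.0 at 37%. That of cumulative incidence is 9.3 and 11.6.

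**The case against.** The strongest reply is Section 8.4. It promises GVHD follow-up after treatment stops for any reason, and if that holds to the horizon the bias is zero. This stands as far as it goes, and a reader should not infer that understatement is built into the plan. But Section 8.4 makes an exception for subjects who discontinue from the study, and Sections 4.2.1 and 5.3.6 take non-responders off the study, not merely off treatment. The documents do not settle which applies.

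Tabulation is also not the same as a crude proportion. The wording covers all secondary outcomes and names no denominator, so this is a gap rather than a stated wrong method. That stands too.

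A reader might infer that the GVHD rate is to be set against the published 37% acute and 17% chronic rates. Those appear only as background in Section 2.8; Section 7 plans no such comparison, test or threshold. A reader might also blame early deaths for the understatement. A patient who dies without GVHD is correctly never a case, so only loss to follow-up lowers the figure.

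Finally, the shifts are small beside the sampling error of 25 patients, and the endpoint is descriptive. That is fair and limits the importance of the point. It does not justify leaving the estimator open.

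**Conclusion.** The point holds as a minor one. The plan gives GVHD incidence no horizon, origin or estimator, and its sections conflict on whether non-responders in cohorts 1 and 2 are followed for it. The size is conditional. If follow-up ends at cycle 6, the crude figure is low by about 3 to 6.5 points at a true 17% and 5 to 13 points at a true 37%. This assumes that 30% to 75% leave at about 5.6 months, a constant hazard, a 12-month horizon and exit independent of GVHD risk. If follow-up reaches the horizon, the bias is nil.

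The stronger reading, that a competing-risks estimator cures the problem at no cost, is not supported. If Section 5.3.6 governs, the later GVHD data do not exist, and exit for non-response may be informative. Primary endpoints and monitoring rules are untouched.

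**What to change.** First reconcile Sections 4.2.1, 5.3.6 and 8.4, so that the protocol says plainly whether GVHD status is collected after a non-responder stops, and for how long.

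Then add a short paragraph to Section 7:

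- Report acute and chronic GVHD as cumulative incidence, with death without GVHD as a competing event and censoring at the last GVHD assessment.
- Use one origin for all patients, the first SGI-110 dose. Do not start the clock at first DLI for recipients and at first dose for the others: Section 4.6.3 plans the first DLI only if no GVHD has been seen, so that grouping depends on the outcome and adds immortal time. Any analysis from first DLI should be descriptive and in recipients only.
- Give 95% intervals at fixed times, for example day 100 and one year, with the counts as a supplement.
- State how relapse and cross-over are handled, how many patients are censored early for non-response, and that this censoring may be informative.

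The cost is GVHD onset and last-assessment dates, the follow-up that Section 8.4 already promises, and wider intervals with at most 25 patients per cohort. No extra patients are needed.
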